6.1 Primary Outcome

The primary outcome is length of hospital stay (time to discharge), measured in number of days, and the primary analysis of the primary outcome will be performed on the full analysis set (FAS). A secondary (sensitivity) analysis of the primary outcome will be performed on the per protocol set (PPS).

Statistical Method for Steps 1-3

The comparison of the length of hospital stay between the NR and placebo groups – in each of the three steps – will be carried out with a Weibull survival model, with time as the number of days of hospital stay and treatment (NR vs placebo) as explanatory variable. The estimated treatment effect will be the hazard ratio (HR) for treatment with a 95% confidence interval.

Presentation of Results

The estimated treatment effect (HR) with a 95% confidence interval will be presented, together with the P-value for the null hypothesis of a zero-treatment difference (HR = 1).

The observed mean and standard deviation for placebo and each dose will be presented in a figure, along with the observed values (length of hospital stay) for each individual, as a scatter with connected lines-plot. Figure 1 shows an example with simulated data.

A plot of the Kaplan-Meier survivor function (for time to discharge) of each dose and placebo will be presented.

[figure not shown]

Figure 1: Simulated data

Missing Data

We will have complete data on the length of hospital stay, except for the following situation: A patient dies before being discharged from the hospital. In this case, the patient will be censored at the time of death. Imputation of the length of hospital stay will be performed as a sensitivity analyses (see item 3 below).

Sensitivity Analyses

The following sensitivity analyses will be performed on the primary outcome:

- 1. As described above but on the per protocol set (PPS)
- 2. As described above but with Cox proportional hazard regression instead of Weibull regression
- As described above but with Cox proportional hazard regression and imputation (instead of censoring) of the length of hospital stay with the maximum length of hospital stay (regardless of treatment group) for patients who die before discharge

Subgroup Analyses

There will be no subgroup analyses.

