2.4 Statistical Framework

The statistical framework will be based on the context of dose-finding, for which there are two main approaches: "regression" and "contrast" (Senn, 2007). In the regression approach, the actual doses used in the trial are viewed as samples from a dose continuum, and the purpose is to estimate the dose response curve. In the contrast approach, interest is on one or (more likely) several contrasts between the doses used in the trial. The former is the most explorative and may be sensitive to modeling choices, small number of doses, and over-fitting, especially for small sample sizes (such as in this trial). The latter is well suited for determining the *minimum effective dose*, in which we compare the different doses to placebo.

Specification of the Primary Objective

The primary objective of this study will be to establish the minimum effective dose of NR on shortening recovery time after critical illness. The primary outcome is length of hospital stay in days (see Section 5.1 for details).

There is only one identified primary analysis in this trial. All other efficacy analyses will be regarded as supportive or exploratory.

Hypothesis Setup

Let μ_1 , μ_2 , μ_3 , and μ_4 denote the mean lengths of hospital stay for placebo, low dose (250 mg/day), medium dose (500 mg/day), and normal dose (1 g/day), respectively.

The statistical scheme to account for multiple testing is based on the *closed multiple test procedure* of Marcus et al. (1976). Under the monotonicity assumption, we define a set of elementary null hypotheses (the many-one comparison) with a preassigned order of performing the tests (Williams, 1971):

Step 1: Test the null hypothesis H_0 : $\mu_1 = \mu_4$ Step 2: Test the null hypothesis H_0 : $\mu_1 = \mu_3$ Step 3: Test the null hypothesis H_0 : $\mu_1 = \mu_2$

The test in Step 1 is carried out with a nominal significance level of α = 0.05. If the test is rejected, the test in Step 2 can be carried out, also with α = 0.05. If the test in Step 2 is rejected, the test in Step 3 can be carried out (with α = 0.05). The tests in steps 2 and 3 are only performed if the preceding null hypothesis is rejected, which – together with the monotonicity assumption – ensures that the significance level is preserved for the entire procedure (Williams, 1971; Bauer, 1991). All tests will be performed two-sided.

Decision Rule

The testing scheme above can result in four situations:

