3.1 Confidence Intervals and P-values

All calculated *P*-values will be two-sided and compared to a 5% significance level. If a *P*-value is less than 0.05, the corresponding treatment group difference will be denoted as statistically significant. All efficacy estimates will be presented with two-sided 95% confidence intervals. The statistical approach to account for multiple testing of three doses versus placebo is the closed multiple test procedure (see Section 2.4). As there is only one primary null hypothesis setup to be tested in this trial, there will be no further adjustments for multiplicity.

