New infections is defined as any infection, mild or serious, occurring between the last point of contact to the next i.e. if a patient has an upper airway infection after discharge, but before the 90 day follow up appointment, this will count as one new infection at the 90 day follow up appointment. The outcome will be the number of new infections per patient, which is a discrete numerical variable.

Re-admissions

Re-admissions is defined as number of all-cause hospital admissions, surgical and medical, up until end of study. The outcome will be the number of new admissions per patient, which is a discrete numerical variable.

Other variables of interest

Metabolites

Rise in NR metabolites from inclusion to day 7 (or discharge if discharged prior to day 7) and until day 90.

Table 1: Overview of outcomes to be reported in the main article. Outcomes to be presented in subsequent articles are listed and defined in the protocol but not shown here.

Level	Outcome	Timeframe	Туре
Primary	Length of hospital stay (to medical fit for discharge)	65 weeks	Time to event
Secondary	Change in grip strength	90 days	Continuous (change from baseline)
	Change in grip strength	7 days	Continuous (change from baseline)
	All-cause mortality	-	Time to event
	Number of new infections per patient	65 weeks	Discrete numerical
	Number of re-admissions per patient	65 weeks	Discrete numerical

6 Statistical Analysis Methods

The overall statistical approach is presented in Section 2.4 and involves 1-3 steps of hypothesis testing and/or estimation of treatment effect. In step 1, only the patients in the normal dose group of NR will be used (in addition to the patients in the placebo group); in Step 2, only the patients in the medium dose group will be used; and in step 3, only the patients in the low dose group will be used. This approach will be followed for the primary and all secondary outcomes. The statistical methods for steps 1-3 will be presented for each type of outcome in the following subsections.

As an exploratory analysis, we will also perform an overall vs. placebo analysis, where the low, medium, and normal dose groups are combined and compared with placebo.

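### With 38 or 28 patients, the uncorrected Weibull test of the primary outcome rejects a true null about 6.2% (step 1) or 6.7% (steps 2 and 3) of the time, not 5%

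*SAP*

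**What the plan says.** SAP 2.4 sets up three ordered tests of dose against placebo, starting with 1 g/day: "The test in Step 1 is carried out with a nominal significance level of α = 0.05". It adds "All tests will be performed two-sided" and "The tests in steps 2 and 3 are only performed if the preceding null hypothesis is rejected". It says that this ordering, together with monotonicity, "ensures that the significance level is preserved for the entire procedure". SAP 3.1 repeats that P "values will be two-sided and compared to a 5% significance level".

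SAP 6 restricts each step to one dose group plus placebo; for example, "in Step 2, only the patients in the medium dose group will be used". SAP Table 1 gives 20, 10 and 10 patients on 1 g, 500 mg and 250 mg per day, and 18 on placebo, pooled over three phases with 6 each.

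Under SAP 6.1 the comparison "will be carried out with a Weibull survival model, with time as the number of days of hospital stay" and treatment as the only explanatory variable. The output is a hazard ratio, a 95% interval and a P value. The section does not say whether the P value is Wald or likelihood-ratio, and it names no exact, resampling or other small-sample method.

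**The concern.** Ordered testing protects the 5% level only if each step is itself a 5% test. Maximum-likelihood Weibull inference relies on large-sample theory, and here it is applied to 38 or 28 patients. The fitted shape is biased upwards at these sizes. The log hazard ratio scales with the fitted shape, but its standard error hardly does, so z is too large and the interval too narrow.

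This is not model misfit, so the checks in SAP 6.5 (proportional hazards, Cox–Snell residuals) cannot reveal it. At stake are the error rate of the only confirmatory analysis, the width of the headline interval, and the reading of a borderline result. In step 1 a large-sample P value between about 0.039 and 0.05 would be called significant although a correctly sized test would not reject.

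**Working it through.** **Inputs.** Weibull stays with scale 18 and shape 2.2, and group sizes 18/10/10/20 (SAP 2.3). Two-sided 5% per step (SAP 2.4). Deaths before discharge are censored (SAP 6.1). The documents give no death rate, so the main case assumes none, with a range of 5–20%.

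**The plan's own figures first.**
- Median: 18 × (ln 2)^(1/2.2) = 15.2. Quartiles: 18 × (−ln 0.75)^(1/2.2) = 10.2 and 18 × (ln 4)^(1/2.2) = 20.9. These agree with the stated 15 and 10–21.
- Power: an MCPMod contrast test on log time at one-sided 2.5% gives 79.0–79.5%, averaged over the three curves. The curve parameters are not in the documents; I assumed an ED50 of 100–500 mg and an exponential delta of 300–500 mg. The stated figure of about 80% reproduces.

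**Mechanism.** For a two-group Weibull model with common shape, z = b/SE, where b is the log hazard ratio. Near the null, SE ≈ √(1/n₁ + 1/n₀):
- 20 v 18: √(0.0500 + 0.0556) = 0.325
- 10 v 18: √(0.1000 + 0.0556) = 0.394

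The mean ratio of fitted to true shape is 1.057 (n = 38) and 1.079 (n = 28). As a rough check, if z is inflated by these factors, the nominal 1.96 acts like 1.96/1.057 = 1.854 (two-sided tail 6.4%) and 1.96/1.079 = 1.816 (6.9%). That is close to the simulated values.

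**Null simulation.** Two-group Weibull maximum likelihood with observed information. The first two rows use 1,000,000 trials per column (Monte Carlo SE about 0.025 points); the other rows use at least 200,000.

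| Rejection of a true null | Step 1 (20 v 18) | Steps 2 and 3 (10 v 18) |
|---|---|---|
| Wald on log HR, cut-off 1.96 | 6.24% | 6.77% |
| Likelihood ratio | 6.09% | 6.52% |
| Wald, 5/10/20% censored by death | 6.2/6.1/6.0% | 6.6/6.6/6.5% |
| Wald, stays rounded up to whole days | 6.5% | 7.1% |
| t reference, n − 3 df (2.030; 2.060) | 5.3% | 5.4–5.5% |
| Simulated cut-off (2.060; 2.106) | 5.0% | 4.9–5.0% |

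Repeat Wald runs of 200,000 or more gave 6.15–6.24% and 6.7–6.8%. Without censoring, the size does not depend on scale or shape. With 380 patients the same code returns 5.0%, so this is an effect of sample size.

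Interval coverage at HR = 1 is one minus the size: about 100 − 6.2 = 93.8% and 100 − 6.7 = 93.3%.

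In 10 v 18 the errors are lopsided: 4.1% falsely favour NR and 2.7% falsely favour placebo.

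**Ordered procedure (Wald, 1.96).**
- No dose works: familywise error 6.2%, all through step 1. The chance of also reaching and rejecting step 2 is 1.1%.
- 1 g/day shortens stay by 33%, 500 mg/day has no effect: step 2 falsely rejects 4.9%.
- 1 g/day has a very large effect (60%), 500 mg/day none: step 2 falsely rejects 6.7%.
- The top two doses have a 60% effect, 250 mg/day none: step 3 falsely rejects 6.7%.

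**The case against.** The excess is 1.2 to 1.8 points in a 58-patient phase II trial, and SAP 2.4 itself calls the level nominal. The SAP does not name Wald or likelihood ratio, so large-sample inference is inferred from the absence of any correction. That stands as a limit on the claim, but the choice between the two tests barely matters.

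The Cox sensitivity analysis in SAP 6.1 estimates no shape parameter. Its Wald size at these numbers is about 5.4% (20 v 18) and 5.6% (10 v 18), so a reader would see a nearly calibrated result beside the primary one. This mitigates the problem, but the Cox analysis is not the primary test.

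Two stronger readings are tempting and should not be drawn:
- A reader might infer that the trial has a 6.7% chance of a false claim for a lower dose. It does not in general. Gatekeeping holds step 2 to 1.1% when no dose works and to 4.9% at the planned 33% effect of 1 g/day.
- A reader might infer that permuting arm labels would give exactly 5% by construction. The design does not support that. Randomisation is blocked within sequential phases (SAP 2.2), and 12 of the 18 placebo patients entered in phases 1 and 2, where 1 g/day was not an option. Free permutation over the 38 patients is valid only if stays did not change between phases. If, for illustration, all phase 3 stays were 10% or 20% shorter with no drug effect, even the calibrated cut-off of 2.06 would reject in about 7.3% or 17% of trials. No small-sample reference repairs that; it is a separate matter.

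**Conclusion.** The point holds as a mild miscalibration of the primary test. Under the SAP's own distribution, step 1 has a size of about 6.2%, and this is also the familywise error when no dose works. The step 2 and 3 tests have a size of about 6.7%, reached in full only when the preceding step is almost certain to reject. The statement in SAP 2.4 that the level is preserved is therefore slightly wrong, and the intervals are somewhat too narrow.

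This rests on exactly Weibull stays, no phase effect, the planned group sizes and large-sample Wald or likelihood-ratio inference. Censoring by death at the assumed rates reduces the excess only slightly. Severity is minor to moderate: it matters for a borderline step 1 result and for the reported intervals. It does not undermine the design or the stated power.

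**What to change.** In SAP 6.1, name one small-sample reference per step and use it for both the P value and the interval, so that the two cannot disagree. Either option serves:

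- **Simulated cut-offs.** Simulate the null distribution of the Weibull z at the actual group sizes, with a fixed seed. The P value is the simulated proportion with |z| at least as large as observed, and the interval is exp(b ± c × SE). At the planned sizes c is about 2.06 (20 v 18) and 2.10 (10 v 18), and the size is about 5.0%. With 5–20% censored the 10 v 18 value is slightly smaller (2.09–2.08).
- **A t reference on n − 3 degrees of freedom.** The P value comes from t and the interval is exp(b ± t × SE), with t = 2.030 (38 patients) or 2.060 (28). It is simpler, with a size of about 5.3% and 5.4–5.5%.

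State whether z is the Wald statistic on the log hazard ratio. If a permutation test is preferred, say that it assumes no phase effect and do not call it exact by construction.

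**Cost.** A few sentences and a few lines of code; Protocol 10.4 allows changes to the plan until database lock. Intervals widen on the log scale by 2.030/1.960 = 1.036 to 2.106/1.960 = 1.074, about 4–7%. Step 1 power at a 33% reduction falls from about 76.5% to about 74% (t) or 73% (simulated cut-off). A 10 v 18 comparison taken alone at 33% falls from 61.8% to about 58% (computed with t on n − 2; slightly lower with either option above).

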#### 5.2 Dosage and Administration

The capsules are taken orally and contain 250 mg of NR or placebo. Placebo or NR capsules will be administered after randomization as described below. (Please also see flow chart under point 5).

- First 16 patients enrolled: 1 capsule 250 mg every morning.
- Following 16 patients enrolled: 1 capsule of 250 mg morning and evening for three months.

- Following 26 patients enrolled: 2 capsules of 250 mg morning and evening for three months.
- High dose of 1000 mg morning and evening has now been cancelled (12.06.2023)

During hospitalizations the capsules will be administered by the hospital personnel while the capsules will be self-administered after discharge. Three months of NR or placebo will be released to the patient at randomization.

The capsules should ideally be swallowed whole, but if necessary, they may be opened before administration and the content poured into a small amount of water for administration in PEG/nasogastric tube. The content should not be chewed or crushed. The absorption of True Niagen remains the same if administered in this fashion, but unusual administration methods will be registered. The capsules may be opened by the hospital staff, but not by the study staff.

Due to strict inclusion criteria, and the expected frailty level of such patients, it is unlikely that two included patients will meet. It is thus unlikely that opening the capsules will lead to patient un-blinding.

A missed dose should be taken as soon as possible, but not any later than 6 hours after the usual time. If more than 6 hours have passed, the patient should wait until the next dose is scheduled.

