2.2 Randomization

Eligible patients are allocated in a 5:3 (phases 1 and 2) or 10:3 (phase 3) ratio between NR and placebo, using a computer randomization procedure. The randomization is blocked within each phase. Details of block size and allocation sequence generation is provided in a separate document unavailable to those who enroll patients or assign treatment.

Details of the randomization including the final random allocation list are held securely and unavailable to unauthorized trial personnel.

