2.3 Sample size

Assuming the time of hospitalization after randomization follows a Weibull distribution with a scale parameter λ = 18 and shape parameter κ =2.2 (corresponding to a median of 15 and an IQR of 10 – 21), we need to include 58 patients: 18 in the placebo group, 10 in the 250 mg/day group, 10 in the 500 mg/day group, and 20 in the 1 g/day group) in order to reach approximately 80% power to show a significant dose-response in this study with a maximal reduction in time of hospitalization of 33%. This calculation is based on optimal designs in dose-finding studies according to the MCPMod methodology with three alternative dose-response curves: linear, e-max and exponential (Pinheiro et al., 2014).

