4.3 Baseline Patient Characteristics

 The patient demographics and baseline characteristics to be summarized include age in years, gender, ethnicity, body mass index, type of accommodation/level of care before admission, smoking status, level of frailty, Charlston score, in-hospital level of care, type of treatment during hospital stay (pressor, respiratory support, 02 supply), diagnosis, SAPSscore, degree of inflammation (highest CRP), mortality and morbidity (number of new organ failures).

Patient demographics and baseline characteristics will be summarized by randomised treatment arm and overall using descriptive statistics for continuous variables, and number and percentages of patients for categorical variables. There will be no statistical analysis of treatment difference. Any clinical important imbalance between the treatment groups will be noted.

5 Definitions of endpoints and Other Variables of Interest

Primary endpoint

Length of Hospital Stay

The length of hospital stay is defined as the number of days from commencing study treatment to medically fit for discharge from the hospital (to home, long term care facility or rehabilitation center or other facility with a lower care level). The term "Medically fit for discharge" is used instead of "discharge" to correct for extended stays due to logistical challenges (Example: medically fit for discharge, but no availability in long term facilities at that time). Only one patient was not discharged on the same day as she/he was medically fit for discharge). Admission to other hospitals after transfer from the first will be included in the total length of stay. The primary outcome will be the time from start of study treatment to discharge. Patients who die before discharge will be censored at the time of death.

Secondary endpoints (safety)

All-cause Mortality

All-cause mortality is a time to event outcome, with the date of randomization as the time when a patient becomes at risk. If a patient does not die during the study's follow-up, the observation is censored at the patient's last automated follow up.

New Infections

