6.5 Assumption Checks and Alternative Analyses

Assumption checks will be performed for the primary and all secondary outcomes according to the statistical methods used to analyzed them.

Weibull and Cox Proportional Hazard Models

The Weibull and Cox proportional hazard regression models assumes that the hazard ratio is constant over time. This will be checked by plotting -log(log(survival)) curves for each treatment against log(analysis time) and assessing if the curves are parallel. If the proportional hazard assumption is deemed to be violated, alternative parametric survival models will be fitted instead. The following survival distributions will be considered: exponential, Gompertz, and lognormal. The goodness-of-fit of each model will be assessed with plots of Cox—Snell residuals against the estimated cumulative hazard function of the residuals, and the one with the best fit will be the chosen model.

Linear Mixed Models

For linear mixed models, we will compare observed and model-predicted outcomes. If we detect a poor-fitting model, we will refit the model with a log-transformation of the outcomes. We do not expect other model-fit problems, due to the simplicity of the model (only a random intercept and a few fixed effects); however, in the unlikely event that we will encounter numerical problems with fitting the model, we will remove the two time point variables and substitute it with a single (linear) variable for time.

Two-sample T test

The discrete numerical outcomes (number of new infections per patient and number of readmissions per patient) are limited to only a few possible values (with no great maximum), and as

such, there is no concern about the distribution of the outcomes, except for the situation where almost all patients have the same number and there is not enough variation in the data to get a meaningful result from the statistical methods. In that case, the outcome will be presented with the table of observed number and percentages in each treatment group in each category only.

7 Safety Analyses

General safety evaluations will be based on the incidence, intensity, and type of AEs, and clinically significant changes in the patient's physical examination findings, vital signs, clinical laboratory results and serum drug concentrations. Safety variables will be tabulated and presented for all patients in the safety set.

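### Step 1 sets 20 phase-3 NR patients against placebo pooled over three sequential phases; the SAP does not state that this needs stays not to differ by phase, and no listed outcome analysis separates phase from dose

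*SAP*

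**What the plan says.** - **Order of enrolment.** Protocol 5.2: "First 16 patients enrolled: 1 capsule 250 mg every morning"; the next 16 and then the next 26 patients go to the two higher dose levels.
- **Randomization.** SAP 2.2: "The randomization is blocked within each phase". SAP 2.1 (Table 1) gives NR and placebo numbers of 10 and 6, 10 and 6, and 20 and 6.
- **One placebo group.** SAP 2.3 counts "18 in the placebo group, 10 in the 250 mg/day group", with 10 and 20 in the other two. SAP 2.4 gives placebo a single mean, μ1, which appears in all three null hypotheses.
- **Step 1.** SAP Section 6 (opening text): "only the patients in the normal dose group of NR will be used (in addition to the patients in the placebo group". Steps 2 and 3 do the same for the medium and low dose.
- **The gate.** Under SAP 2.4, failure to reject in step 1 leads to the conclusion that none of the studied doses works, and "The tests in steps 2 and 3 are only performed if the preceding null hypothesis is rejected".
- **Model.** SAP 6.1 fits a Weibull model "with time as the number of days of hospital stay and treatment (NR vs placebo) as explanatory variable". Phase is not a term.
- **Checks.** The sensitivity analyses in SAP 6.1 use the per-protocol set, Cox regression, or Cox regression with imputation for deaths. No subgroup analyses are planned. SAP 6.5 examines "curves for each treatment against log(analysis time) and assessing if the curves are parallel". Under SAP 4.3, baseline data are "summarized by randomised treatment arm and overall using descriptive statistics for continuous variables".

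The only assumption stated with the testing scheme is a monotone dose response.

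**The concern.** Each NR dose was given in one phase only, so dose and enrolment period coincide within NR. All 20 normal-dose patients belong to phase 3, but only 6 of the 18 placebo patients were randomized alongside them. The other 12 entered earlier, when that dose was not on offer. The step-1 hazard ratio is therefore partly a randomized comparison (20 v 6) and partly a comparison across periods.

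If stays differ between phases for reasons other than treatment, a treatment-only model credits part of that difference to NR. Shorter stays in phase 3 would look like benefit; longer ones would hide it. Step 1 carries the trial's conclusion, so an error there is not corrected later in the sequence.

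**Working it through.** **1. The plan's own figure.** Inputs from SAP 2.3: Weibull scale 18, shape 2.2, groups of 18/10/10/20, maximal reduction 33%. The computed median is 15.2 and the IQR 10.2–20.9, in line with the stated 15 and 10–21. An MCPMod maximum-contrast test on the log-time scale, with variance 1/(2.2² × n) per group and one-sided 2.5%, gives mean power of 0.79–0.80 over five assumed sets of e-max and exponential parameters (the documents give none). The stated 80% is thus reproduced, and it uses all 18 placebo patients.

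**2. Step 1 as planned.** A 33% shorter stay is a discharge HR of (1/0.67)^2.2 = 2.41, log HR 0.881. The standard error for 20 v 18 is √(1/20 + 1/18) = 0.325. Power is Φ(0.881/0.325 − 1.96) = Φ(0.75) = 77%, and 77% in simulation. The significance limit is exp(1.96 × 0.325) = 1.89.

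**3. How drift enters.** Let phase-3 stays alone be shorter by a fraction x, with no drug effect. Two thirds of the log-hazard shift passes into the estimate: log HR = (12/18) × 2.2 × ln(1/(1 − x)).
- x = 0.05: 0.075, HR 1.08
- x = 0.10: 0.155, HR 1.17
- x = 0.20: 0.327, HR 1.39

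For an even trend with stay multipliers 1, 1 − x/2, 1 − x, about half passes through. At x = 0.20: 2.2 × [(ln 1 + ln 0.9 + ln 0.8)/3 − ln 0.8] = 0.250, HR 1.28. At x = 0.10 the HR is 1.12.

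**4. Error rates for step 1.** Simulated Weibull maximum likelihood, Wald test at 1.96, no deaths. Every drift size is an assumption.

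| Drift | False favourable rate, no drug effect (phase 3 shorter) | Power at 33% reduction (phase 3 longer) |
|---|---|---|
| None | about 3% | 76–77% |
| Abrupt 5% | about 5% | not run |
| Abrupt 10% | about 8% | about 62% |
| Abrupt 20% | about 19% | about 49% |
| Even trend to 10% | about 6% | about 66% |
| Even trend to 20% | 13–14% | about 56% |

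The 3% without drift, against a nominal 2.5%, is a small-sample effect and a separate matter. The way drift is expressed also counts: phases 1–2 20% longer than phase 3 (ratio 1.20) gives 14.5%, while phase 3 20% shorter (ratio 1.25) gives 19%. For drift alone to place the expected HR at 1.89, an abrupt shift would have to reach 35%: (2/3) × 2.2 × ln(1/0.648) = 0.637 = ln 1.89.

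**5. Steps 2 and 3.** The gate limits the damage. With no effective dose, a 20% shortening in phase 1 or phase 2 alone yields a false low- or medium-dose declaration in about 0.5% of trials or fewer. The largest rate in any no-effect pattern simulated was 2.1% (phases 2 and 3 both 20% shorter). Step 2 matters mainly if step 1 is truly positive. If only the normal dose works, phase-2 stays 10% or 20% shorter raise a false medium-dose declaration from 3.9% to 7.5% or 13.5%.

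**6. Exploratory all-NR comparison.** Half of NR (20/40) and a third of placebo (6/18) are in phase 3. An abrupt 20% shift gives 2.2 × 0.223 × (1/2 − 1/3) = 0.082, HR 1.085: minor.

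**7. What the planned outputs would reveal.** The three sensitivity analyses keep all 18 placebo patients as one group, or whichever of them are in the per-protocol set. The proportional-hazards plot is by treatment over time in hospital, not by calendar time. The stay plots and Kaplan-Meier curves are by dose and placebo. None of these outcome analyses separates phase from dose.

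**The case against.** **Pooling is a deliberate choice.** The sample size rests on 18 placebo patients, and the single mean μ1 implies a common placebo distribution. This stands, and it is why the pooled analysis should stay primary. It does not replace a statement that μ1 must be the same in every phase.

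**The baseline table helps.** If the arms in SAP 4.3 are the four dose groups, each NR column is one phase, and the table includes SAPS score, frailty and comorbidity. SAP 4.3 also promises to note clinically important imbalance. Case-mix drift would then partly show, so it would be too strong to say that the planned report could reveal nothing. The table still does not split the 18 placebo patients, and it shows no effect on stay.

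**No drift is shown.** A reader might infer drift from the relaxed liver-enzyme exclusion, the option to add wards or hospitals (Protocol 4.1), or the pandemic. The documents do not support that. The exclusion text is dated November 2020 but is listed for ethics submission in June 2023, so the phase it affected is not established. Adding wards is only permitted. The pandemic remark concerns recruitment pace. Some features work against drift: patients must be stable and expected to stay at least 7 more days (Protocol 4.3), and the SAP endpoint of fitness for discharge removes logistical delay, although the SAP says this changed the date for one patient only.

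**The check is weak.** This also stands; its limits are given with the fix.

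**Conclusion.** The point holds as a gap in statement and sensitivity analysis. Step 1 depends on stays not differing by phase apart from treatment. The SAP implies this without saying it, and no listed outcome analysis examines it. Drift of 5% matters little (about 5% false favourable against 3%). Drift of 10% to 20% would matter: 8% to 19% if abrupt, about 6% to 14% if an even trend, with power down to about 62% or 49% for abrupt drift in the other direction. These figures rest on the SAP's Weibull parameters, no deaths, and assumed drift.

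A reader might go further and conclude that the primary analysis is invalid or should be replaced by the same-phase comparison. The documents do not support that: they contain no data on drift, and the replacement would cut power from 77% to about 45%.

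**What to change.** Keep the pooled-placebo analysis and the decision rule unchanged.

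1. **SAP 6.1.** State the assumption, for example: *Each dose group is compared with placebo patients from all three phases; this assumes that, apart from treatment, length of stay does not differ between phases.* Add a fourth sensitivity analysis, chiefly for step 1, against same-phase placebo only (20 v 6) or with a phase term, reported as HR with 95% CI outside the decision rule. In step 1 the two are nearly the same, because phases 1 and 2 contribute placebo patients only. State the limits with it:
   - Power is about 45% (47% with a phase term).
   - The CI is the HR times or divided by exp(1.96 × √(1/20 + 1/6)) = 2.5, against 1.9 pooled.
   - Information n1·n0/(n1 + n0) falls from 20 × 18/38 = 9.47 to 20 × 6/26 = 4.62, a 51% loss.
   - In simulation its false favourable rate stayed near 2% in every drift pattern. It discloses how far the result relies on the assumption but cannot prove absence of drift.
2. **SAP Section 6.** Stratify the exploratory all-NR v placebo analysis by phase, the unit within which patients are randomized. For that 40 v 18 comparison only, information goes from 40 × 18/58 = 12.41 to 3.75 + 3.75 + 4.62 = 12.12, a 2.4% cost.
3. **Optional.** Show placebo length of stay and baseline severity by phase (6, 6, 6). This is descriptive: phase 3 against phases 1–2 (6 v 12) gives 95% limits of the stay ratio times or divided by exp(1.96 × √(1/6 + 1/12)/2.2) = 1.56, and about 20% power for a 20% shift.

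No new data are needed. The subject number identifies the phase (Protocol 5.8), and the plan may be amended until database lock (Protocol 10.4).
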